### 10.5. Appendix 5: Standard Discontinuation Criteria

CDISC Submission Value	CDISC Definition
Adverse event	Any untoward medical occurrence in a patient or clinical investigation subject administered a pharmaceutical product and which does not necessarily have a causal relationship with this treatment. An adverse event (AE) can therefore be any unintended sign (including an abnormal laboratory finding), symptom, or disease temporally associated with the use of a medicinal (investigational) product, whether or not related to the medicinal (investigational) product. For further information, see the ICH Guideline for Clinical Safety Data Management: Definitions and Standards for Expedited Reporting (modified from ICH E2A) Synonyms: side effect, adverse experience. See also serious adverse event, serious adverse experience. (CDISC glossary)
Completed	To possess every necessary or normal part or component or step; having come or been brought to a conclusion (NCI)
Death	The absence of life or state of being dead (NCI)
Lost to follow-up	The loss or lack of continuation of a subject to follow-up
Other	Different than the one(s) previously specified or mentioned (NCI)
Physician decision	A position, opinion or judgment reached after consideration by a physician with reference to subject (NCI)
Pregnancy	Pregnancy is the state or condition of having a developing embryo or fetus in the body (uterus), after union of an ovum and spermatozoon, during the period from conception to birth. (NCI)
Protocol deviation	An event or decision that stands in contrast to the guidelines set out by the protocol (NCI)
Screen failure	The potential subject who does not meet one or more criteria required for participation in a trial
Site terminated by sponsor	An indication that a clinical study was stopped at a particular site by its sponsor (NCI)
Study terminated by sponsor	An indication that a clinical study was stopped by its sponsor (NCI)
Withdrawal by subject	An indication that a study participant has removed itself from the study (NCI)

Approval Date: 12-Feb-2021 17:39:44 (GMT)

Relamorelin

### 10.6. Appendix 6: Study Tabular Summary

Parameter Group	Parameter	Value
Trial information	Trial Title	Open-label Extension Study of Relamorelin for the Treatment of Diabetic Gastroparesis
	Clinical Study Sponsor	Allergan
	Trial Phase Classification	Phase 3 Trial
	Trial Indication	DG
	Trial Indication Type	Treatment
	Trial Type	Safety
	Trial Length	Until the product becomes commercially available or the sponsor terminates development
	Planned Country of Investigational Sites	multiple
	Planned Number of Subjects	~1000
	FDA-Regulated Device Study	No
	FDA-Regulated Drug Study	Yes
	Pediatric Study	No
Subject information	Diagnosis Group	NA
	Healthy Subject Indicator	No
	Planned Minimum Age of Subjects	18 years
	Planned Maximum Age of Subjects	NA
	Sex of Participants	Both
	Stable Disease Minimum Duration	3 months
Treatments	Investigational Therapy or Treatment	RLM
	Intervention Type	Drug
	Pharmacological Class of Invest. Therapy	Synthetic ghrelin analogue
	Dose per Administration	10
	Dose Units	µg
	Dosing Frequency	BID
	Route of Administration	SC
	Current Therapy or Treatment	RLM
	Added on to Existing Treatments	No
	Control Type	N/A
Comparative Treatment Name	N/A	
Trial design	Study Type	Interventional
	Intervention Model	Open-label
	Planned Number of Arms	1
	Trial is Randomized	No
	Randomization Quotient	N/A
	Trial Blinding Schema	N/A
	Stratification Factor	N/A
	Adaptive Design	No
Study Stop Rules	No	

Approval Date: 12-Feb-2021 17:39:44 (GMT)

Relamorelin

## 10.7. Appendix 7: Contraceptive Guidance and Collection of Pregnancy Information

### Definitions

#### Women of Child Bearing Potential (WOCBP)

A woman is considered fertile following menarche and until becoming postmenopausal unless permanently sterile (see below).

#### Women in the following categories are not considered WOCBP:

1. Premenarchal
2. Premenopausal female with 1 of the following:
  - Documented hysterectomy
  - Documented bilateral salpingectomy
  - Documented bilateral oophorectomy

Note: Documentation can come from the site personnel's: review of the participant's medical records, medical examination, or medical history interview.

[figure not shown]
3. Postmenopausal female
  - A postmenopausal state is defined as no menses for 12 months without an alternative medical cause. A high FSH level in the postmenopausal range may be used to confirm a postmenopausal state in women not using hormonal contraception or HRT. However, in the absence of 12 months of amenorrhea, a single FSH measurement is insufficient.
  - Females on HRT and whose menopausal status is in doubt will be required to use one of the non-hormonal highly effective contraception methods if they wish to continue their HRT during the study. Otherwise, they must discontinue HRT to allow confirmation of postmenopausal status before study enrollment.

[figure not shown]
CONFIDENTIAL  
Relamorelin

[figure not shown]
Protocol 3071-305-020 Amendment 2

**Contraception Guidance**

Approval Date: 12-Feb-2021 17:39:44 (GMT)

Relamorelin

## 10.8. Appendix 8: Medical Device Incidents: Definition and Procedures for Recording, Evaluating, Follow-up, and Reporting

### 10.8.1. Definitions of a Medical Device Incident

The detection and documentation procedures described in this protocol apply to all sponsor medical devices provided for use in the study (see Section 6.1 for the list of sponsor medical devices).

#### Medical Device Incident Definition

- A medical device incident is any malfunction or deterioration in the characteristics and/or performance of a device as well as any inadequacy in the labeling or the instructions for use which, directly or indirectly, might lead to or might have led to the death of a participant/user/other person or to a serious deterioration in his/her state of health.
- Not all incidents lead to death or serious deterioration in health. The nonoccurrence of such a result might have been due to other fortunate circumstances or to the intervention of health care personnel.

#### It is sufficient that:

- An **incident** associated with a device happened.

AND

- The **incident** was such that, if it occurred again, might lead to death or a serious deterioration in health.

A serious deterioration in state of health can include any of the following:

- Life-threatening illness
- Permanent impairment of body function or permanent damage to body structure
- Condition necessitating medical or surgical intervention to prevent one of the above
- Fetal distress, fetal death, or any congenital abnormality or birth defects

**Examples of Incidents**

- A participant, user, caregiver, or healthcare professional is injured as a result of a medical device failure or its misuse.
- A participant’s study intervention is interrupted or compromised by a medical device failure.
- A misdiagnosis due to medical device failure leads to inappropriate intervention.
- A participant’s health deteriorates due to medical device failure.

**10.8.2. Documenting Medical Device Incidents**

**Medical Device Incident Documenting**

Relamorelin

### 10.9. Appendix 9: Liver Safety: Suggested Actions and Follow-up Assessments

Close monitoring should be initiated for the following participants:

- Participants with normal baseline serum aminotransferases (AT) who develop an increase of serum AT  $\geq 3 \times$  ULN
- Participants with elevated baseline AT who develop an increase of serum AT  $> 2 \times$  the baseline value

The participant should return to the study site and be evaluated for potential drug-induced liver injury (DILI) as soon as possible, preferably within 48 to 72 hours from the time the investigator becomes aware of the abnormal results. Evaluation should typically include repeat testing of all 4 of the usual serum biochemical measures (ALT, AST, ALP, and TBL) to confirm the abnormalities and to determine if they are increasing or decreasing.

If it is difficult for the participant to return to the study site promptly, the participant should be retested locally, but normal laboratory ranges should be recorded, results should be made available to sponsor's study physician and the investigator immediately, and the data should be included in the eCRF. If repeat testing within this time frame is not possible, the study intervention should be discontinued.

It is critical to initiate close monitoring immediately upon detection and confirmation of signals of potential DILI as early as possible and not to wait until the next scheduled visit or monitoring interval. Close monitoring of the participant should be initiated in conjunction with the sponsor and consideration given to the following:

- Obtain a more detailed history of symptoms and prior or concurrent diseases.
- Obtain a history of concomitant drug use, including nonprescription medications, herbal products and dietary supplements, alcohol and recreational drug use, and special diets.
- Obtain a history of exposure to environmental chemical agents.
- Initiation of appropriate evaluations including applicable laboratory tests (eg, direct bilirubin, INR), physical assessments, and other assessments (eg, imaging)
  - o Rule out other potential causes of biochemical abnormalities, eg, acute viral hepatitis types A, B, C, D, and E; autoimmune or alcoholic hepatitis; NASH; hypoxic/ischemic hepatopathy; and biliary tract disease.
- Consider gastroenterology or hepatology consultations.

If any of the following criteria are met, discontinuation of study intervention should be considered (if indicated, prior to receipt of confirming retest biochemistry laboratory test results) and the sponsor notified of the discontinuation:

- ALT or AST  $\geq 3 \times$  ULN and the participant is symptomatic with the appearance of fatigue, nausea, vomiting, right upper quadrant pain or tenderness, fever, rash, or eosinophilia ( $> 5\%$ )
- ALT or AST  $\geq 3 \times$  ULN and total bilirubin  $> 2 \times$  ULN or INR  $> 1.5$

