## Relamorelin

- ALT or AST  $\geq 5 \times$  ULN for more than 2 weeks
- ALT or AST  $\geq 8 \times$  ULN

If the study intervention is discontinued, the participant may be re-challenged with study intervention only after consultation with the Allergan MSP. All participants showing potential DILI should be followed until all abnormalities return to normal or to the baseline state.

[figure not shown]

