**Reporting of Potential Hy's Law Cases**

[figure not shown]
Potential Hy's law cases are defined by biochemical test results of hepatocellular injury and impaired hepatic function. They are considered Adverse Events of Special Interest (AESIs) and should be evaluated and followed further (ie, close monitoring initiated) to determine whether these laboratory abnormalities are indicative of DILI. As indicated above, discontinuation of study intervention should also be considered. Criteria that identify a potential Hy's law case are as follows:

- ALT or AST  $\geq 3 \times$  ULN AND
- Total bilirubin  $\geq 2 \times$  ULN AND
- Alkaline phosphatase  $< 2 \times$  ULN

Sites must report every participant who meets the Hy's law criteria if this occurs within the time the participant signs the ICF until 30 days after the last dose of study intervention.

[figure not shown]
A laboratory alert for a potential DILI case will be sent immediately to the sponsor and investigators when the above criteria have been met, even if no clinical symptoms have been experienced.

[figure not shown]

[figure not shown]

[figure not shown]

[figure not shown]

Relamorelin

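### Appendix 9: the early-retest trigger for raised baseline aminotransferases has no ULN ceiling, so with a baseline above 2.5 × ULN a rise to 5 × ULN can prompt no timed retest

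*Protocol*

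**What the plan says.** All of this is in Protocol Section 10.9 (Appendix 9) unless stated otherwise.

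- **Close-monitoring list.** There are two groups. Participants with normal baseline aminotransferases (AT) enter at ≥ 3 × ULN. The second group is "Participants with elevated baseline AT who develop an increase of serum AT" to > 2 × the baseline value. Those listed should return for repeat ALT, AST, ALP and total bilirubin, "preferably within 48 to 72 hours from the time the investigator becomes aware of the abnormal results". Local retesting is allowed if a prompt return is difficult. A fallback follows: "If repeat testing within this time frame is not possible, the study intervention should be discontinued".
- **Criteria for considering discontinuation.** These are fixed ULN multiples at any baseline: ≥ 3 × ULN with symptoms; ≥ 3 × ULN with raised bilirubin or INR; ≥ 5 × "ULN for more than 2 weeks"; and ≥ 8 × ULN. Stopping may be considered, "if indicated, prior to receipt of confirming retest biochemistry laboratory test results".
- **General text.** Sites are told to act on "signals of potential DILI as early as possible and not to wait until the next scheduled visit or monitoring interval". Also, "All participants showing potential DILI should be followed until all abnormalities return to normal or to the baseline state". Potential Hy's law cases, at any baseline, "should be evaluated and followed further (ie, close monitoring initiated) to determine whether these laboratory abnormalities are indicative of DILI".
- **Section 8.2.4.** Abnormal values judged clinically significant must be repeated. No time is set.

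**The concern.** The monitoring trigger for a raised baseline scales with that baseline, while the stopping criteria do not. Once the baseline is high enough, a value can reach a level named in the stopping criteria without having doubled. The participant is then outside the list that carries the 48-to-72-hour retest and its fallback.

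This matters most for the persistence criterion, because a single result can never meet it. If the next value comes only at the next scheduled visit, the question of whether AT has stayed at or above 5 × ULN for over 2 weeks is answered late. The timing then depends on how each site reads the general sentences. With about 1000 participants at about 700 sites (Section 4.1), roughly 1.4 per site, explicit triggers are worth having.

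**Working it through.** No figure in the protocol needs reproducing; the check is threshold arithmetic.

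**Inputs.** Let b be baseline AT in multiples of ULN, with b > 1. From Appendix 9, the listed trigger is AT > 2b, the persistence criterion starts at 5, and a further criterion applies at 8 whatever the duration.

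**Where the gap starts.** A value of at least 5 that does not exceed 2b is off the list. This needs 2b ≥ 5, so b ≥ 5/2 = 2.5. At b = 2.5 only the single value 5.0 is missed; above that there is a band.

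**Band that bears on the persistence criterion alone.** It runs from max(5, b) to min(2b, 8). Values must be above baseline and below 8. The fold rise is AT/b.

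| Baseline (× ULN) | Listed trigger (× ULN) | Off the list, persistence criterion only (× ULN) | Fold rise over baseline |
|---|---|---|---|
| 2.4 | > 4.8 | none | – |
| 2.6 | > 5.2 | 5.0 to 5.2 | 1.92 to 2.0 |
| 3.0 | > 6.0 | 5.0 to 6.0 | 1.67 to 2.0 |
| 3.5 | > 7.0 | 5.0 to 7.0 | 1.43 to 2.0 |
| 4.0 | > 8.0 | 5.0 to below 8.0 | 1.25 to just under 2.0 |
| 4.5 | > 9.0 | 5.0 to below 8.0 | 1.11 to under 1.78 |
| 5.0 | > 10.0 | above 5.0 to below 8.0 | above 1.0 to under 1.6 |

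For example, at b = 3.0 the lower end is 5/3 = 1.67-fold and the upper end is 6/3 = 2.0-fold.

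**Reading of the trigger.** The table takes the phrase to mean the level reached. If it means a rise *by* more than 2 × baseline, the trigger is AT > 3b and the gap starts at b = 5/3 = 1.67. The table therefore uses the reading kinder to the protocol.

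**Time to the next scheduled value.** Section 8.2.3 puts Visit 5 at Month 12. Visit 1 is baseline, so leaving Visit 1a at Week 2 aside there are four intervals in 12 months: 12/4 = 3 months on average, about 13 weeks, against a 2-week persistence window. The revised footnote A in the Amendment 2 summary gives 3-monthly laboratory tests after Month 12. The Schedule of Activities is not shown, so the first-year spacing is an inference.

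**With a 5 × ULN ceiling.** For b below 2.5 the listed threshold stays at > 2b. For b from 2.5 to below 5 it becomes ≥ 5. For b of 5 or more it becomes any rise above baseline. The band closes.

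**The case against.** The strongest reply is that nothing here is contradictory. One list says whom to watch closely and the other says when to consider stopping; neither has to contain the other. A value above baseline at 5 × ULN, a level the appendix itself names, would naturally be read as a signal of potential DILI, and sites are told not to wait on such signals. A criterion with a duration implies a second measurement. Section 8.2.4 makes repeats mandatory for clinically significant values, and Section 8 sends immediate safety concerns to the sponsor at once.

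Much of this stands, and it is why the point is small. What it does not supply is a retest time. The instruction not to wait gives no threshold for this group. Section 8.2.4 depends on the investigator's judgement, and it generally excludes findings associated with the underlying disease. The Hy's law route also needs bilirubin ≥ 2 × ULN with ALP < 2 × ULN.

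The affected group is also narrow. Exclusion 3 lets the investigator keep out participants with hepatic disease, and exclusion 2 those with a limiting unresolved adverse event. Section 2.2 reports no clinically relevant liver-test abnormalities in the Phase 2b study. But the entry criteria set no numeric AT limit, and Appendix 9 itself provides for raised baselines.

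A reader might infer that the other stopping criteria leave the same hole: ≥ 8 × ULN from baselines above 4, and ≥ 3 × ULN with symptoms from baselines above 1.5. The thresholds are misaligned there too. However, once such a criterion is met the appendix already prompts a stop decision and presupposes a confirming retest. Those criteria do not need adding to the list.

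**Conclusion.** The gap is real and minor. With baseline AT above 2.5 × ULN, a rise to between 5 × ULN and 2 × baseline carries no listed, timed retest, although the persistence criterion cannot be assessed without a second value.

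Two stronger conclusions are not supported. It would be wrong to say that a mandatory stop is missed: the appendix is headed as suggested actions, and stopping is only to be considered. It would also be wrong to say that these participants have no route to a retest, because the general text provides one without a set time.

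The conclusion rests on the thresholds as printed, on the level-reached reading of the trigger, and on an inferred visit spacing of about 3 months. Some Appendix 9 figures and the Schedule of Activities are not shown. The document gives no frequency of baselines above 2.5 × ULN; the number affected is unknown and probably very small.

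**What to change.** Reword the second close-monitoring bullet in Appendix 9 so that, for a raised baseline, it applies when *serum AT rises to > 2 × the baseline value, or rises above baseline to ≥ 5 × ULN, whichever is lower*. The phrase *rises to* also settles that the level reached is meant.

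Do not add the remaining discontinuation criteria to the list. One of them is ≥ 3 × ULN with symptoms that include nausea or vomiting, which are core symptoms of diabetic gastroparesis. Listing it could bring participants stable at 3 to 5 × ULN under the fallback stop.

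The cost is one edited bullet and a few extra retests at baselines above 2.5 × ULN. Some will follow small rises: a move from 4.9 to 5.0 × ULN is a 2% rise (0.1/4.9) and would qualify. Those participants would also come under the fallback that study intervention should be discontinued if a timely retest, on site or local, is not possible. Local retesting should keep such stops rare. Participants with baselines below 2.5 × ULN are unaffected.

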## Relamorelin

- ALT or AST  $\geq 5 \times$  ULN for more than 2 weeks
- ALT or AST  $\geq 8 \times$  ULN

If the study intervention is discontinued, the participant may be re-challenged with study intervention only after consultation with the Allergan MSP. All participants showing potential DILI should be followed until all abnormalities return to normal or to the baseline state.

[figure not shown]

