**7.1. Discontinuation of Study Intervention**

**7.1.1. Temporary Discontinuation**

In the event of AE or intercurrent illness, dosing of study intervention can be stopped temporarily for a maximum duration of 14 days. If longer cessation of dosing is necessary, the investigator must contact the sponsor.

Relamorelin

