### 7.1.2. Permanent Discontinuation

Permanent discontinuation of study intervention also requires discontinuation from the study. The following criteria should be evaluated:

- Special consideration should be paid to the appearance of abnormal laboratory test results suggesting severe drug-induced liver injury (DILI). Discontinuation of study intervention for abnormal liver function should be considered by the investigator when a participant meets criteria for Hy's law (see Section 8.3.7.1 and Appendix 9) or if the investigator believes that it is in the best interest of the participant.
- Documented episode of diabetic ketoacidosis, hyperosmolar non-ketotic diabetic syndrome, or severe hypoglycemia (defined as glucose levels < 3mmol/L, or < 54 mg/dl) that are assessed as study treatment-related.
- Female participants who become pregnant during the study must be discontinued from study intervention immediately and withdrawn from the study. See Appendix 7 for further details regarding follow-up of the participant through the pregnancy.

See the SoA (Section 1.3) for data to be collected at the time of study intervention discontinuation.

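### For potential Hy's law cases, Section 7.1.2 makes a liver-related stop permanent with exit from the study, while Appendix 9 allows re-challenge after a stop it never calls temporary

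*Protocol*

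**What the plan says.** Three places in the protocol bear on a liver-related stop.

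- **Section 7.1.2 (Permanent Discontinuation)** opens with its consequence: "Permanent discontinuation of study intervention also requires discontinuation from the study". The first criterion under that heading reads "Discontinuation of study intervention for abnormal liver function should be considered by the investigator when a participant meets criteria for Hy's law". It extends to a stop that the investigator believes is in the participant's best interest, and it directs the reader onward: "see Section 8.3.7.1 and Appendix 9".
- **Appendix 9 (Section 10.9)** lists four liver criteria at which discontinuation should be considered. Its part on potential Hy's law cases ties them to that text: "As indicated above, discontinuation of study intervention should also be considered". On what follows a stop it says: "the participant may be re-challenged with study intervention only after consultation with the Allergan MSP".
- **Section 7.1.1 (Temporary Discontinuation)** provides that, for an AE or intercurrent illness, "dosing of study intervention can be stopped temporarily for a maximum duration of 14 days". A longer pause requires contact with the sponsor. The section mentions neither liver events nor Appendix 9.

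**The concern.** A cross-reference joins two instructions with different outcomes. Under Section 7.1.2 a participant stopped for a potential Hy's law event has left the study. Under Appendix 9 the same participant may receive study intervention again after consultation with the sponsor's Medical Safety Physician (MSP). The supplied protocol text describes no route back into the study after discontinuation from it, so both instructions cannot apply to one stop.

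Safety is the study's only objective (Section 3). Three things depend on which instruction a site follows:

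- whether the participant is withdrawn or continues;
- whether the event appears in the summary of TEAEs leading to discontinuation (Section 9.4.1.1);
- the date of last dose. That date closes the 30-day TEAE window (Section 9.4.1.1) and the 30-day reporting window for potential Hy's law cases (Section 8.3.7.1 and Appendix 9).

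**Working it through.** The protocol gives no figure to reproduce. The check is a comparison of text.

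**Step 1: do the two sections cover the same participants?** Sections 8.3.7.1 and Appendix 9 define a potential Hy's law case identically: ALT or AST ≥ 3 × ULN, total bilirubin ≥ 2 × ULN and alkaline phosphatase < 2 × ULN. Section 7.1.2 names Hy's law and cites both. Take a participant with ALT ≥ 3 × ULN, bilirubin > 2 × ULN and alkaline phosphatase < 2 × ULN. This participant meets:

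- the named liver criterion of Section 7.1.2;
- the listed Appendix 9 criterion that combines ALT or AST ≥ 3 × ULN with bilirubin > 2 × ULN or INR > 1.5;
- the Hy's law paragraph of Appendix 9, which refers back to discontinuation.

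The overlap is exact for Hy's law cases. The other Appendix 9 criteria are ALT or AST ≥ 3 × ULN with symptoms, ≥ 5 × ULN for more than 2 weeks, and ≥ 8 × ULN. These can be met without Hy's law and reach Section 7.1.2 only through its best-interest clause.

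**Step 2: what follows once the investigator stops dosing?**

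| | Section 7.1.2 | Appendix 9 |
|---|---|---|
| Strength of the instruction to stop | to be considered | to be considered |
| Label on the stop | permanent | none |
| Place in the study | participant leaves | not stated |
| Further dosing | none described | possible after MSP consultation |
| Exception for Hy's law cases | not applicable | none |

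**Step 3: does another passage settle it?** Section 7.1.1 could, if the Appendix 9 stop were a temporary one. Neither passage says so. Appendix 9 does not cite 7.1.1, and 7.1.1 does not cite Appendix 9. Of the two discontinuation sections, only the permanent one refers to Appendix 9. Where the protocol intends a permanent stop it can say so plainly: Section 8.3.7.2 does this for treatment-related ketoacidosis, hyperosmolar syndrome and severe hypoglycemia. Appendix 9 also contains a firmer, equally unlabelled instruction to discontinue when repeat testing cannot be done in time.

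**Step 4: size.** The protocol gives no expected rate of liver events, so the number of cases cannot be calculated. Two figures give scale:

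- About 1000 participants at about 700 sites is 1000 / 700 ≈ 1.4 per site. Few sites would have handled a comparable case before, so uniform handling rests on the text.
- If about 1000 participants enter the safety population, each case classified one way rather than the other moves the percentage with TEAEs leading to discontinuation by 1 / 1000 = 0.1 percentage points.

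**The case against.** The strongest reply is that a coherent reading exists. Section 7.1.1 covers a pause for any AE, liver events included. Section 7.1.2 requires exit only when the stop is permanent. Appendix 9 is titled as suggested actions and never uses the word permanent. Dosing would be paused and the MSP consulted, and the participant would then be either re-challenged or permanently discontinued. MSP consultation would parallel the sponsor contact in 7.1.1. That reading is possible and may be what was meant, but the protocol does not state it, and the liver criterion that cites Appendix 9 sits under the permanent heading.

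A second reply is that stopping is discretionary in both places. That is true of the decision to stop. The conflict concerns what happens after it.

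A reader might also infer four stronger things that the protocol does not support:

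- **A clash with the 14-day limit.** One Appendix 9 criterion needs an elevation lasting more than 2 weeks, but that is the duration of the enzyme elevation before a stop is considered. The 14 days limit the pause in dosing, and 7.1.1 allows longer with sponsor contact. The two do not conflict.
- **Every affected case is an AESI.** Appendix 3 names Hy's law cases as the liver AESI. Three of the four Appendix 9 criteria can be met without being one.
- **Safety follow-up is lost.** Appendix 9 requires participants with potential DILI to be followed until values return to normal or baseline. Section 8.3.3 requires follow-up of AEs and SAEs to resolution or stabilization, and Section 8.3.7.1 requires potential Hy's law cases to be reported as SAEs. None of these depends on how the stop is labelled.
- **The protocol should specify table coding.** That can be left to the SAP, which is not at hand.

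**Conclusion.** The point stands for potential Hy's law cases and for participants stopped for abnormal liver function in their best interest. Section 7.1.2 and Appendix 9 give such a participant, once stopped, two outcomes that cannot both apply, and nothing in the protocol chooses between them. It would go too far to say that every participant meeting an Appendix 9 criterion falls under both rules, or that the temporary-stop reading is excluded. That reading is available but unstated.

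The likely effect is inconsistent handling and classification of a small number of cases. Each one is visible in a safety-only study with its own table of TEAEs leading to discontinuation. The potential Hy's law cases remain reportable as SAEs either way.

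The conclusion rests on the current text of Sections 7.1.1, 7.1.2 and 8.3.7.1 and Appendix 9. The Schedule of Activities, to which Section 7.1.2 refers for data collected at discontinuation, was not in the text available. The change should be made, although no efficacy or hypothesis test depends on it.

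**What to change.** Reconcile Sections 7.1.1 and 7.1.2 with Appendix 9. For each liver-related stop in Appendix 9, including the one that applies when timely repeat testing is not possible, identify whether it is an interruption or a permanent discontinuation. State whether the participant stays in the study while re-challenge is being considered. Make the cross-reference from Section 7.1.2 agree with the result, and add one from 7.1.1 if any of these stops belongs there. Which clinical rule applies is for the sponsor to decide; none is proposed here.

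The cost is wording in two or three sections of the next amendment. No new assessments or data collection are implied.
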